6.7 Ancillary Analyses/Sensitivity Analyses

[figure not shown]
Ancillary analyses will be undertaken in the form of secondary and tertiary analyses. No formal hypotheses testing will be conducted for the ancillary analyses.

6.7.1.1 Secondary Analyses

All secondary analyses will be presented using descriptive statistics and analyzed using pairwise correlations to compare the mean score of the cochlear implant Arm A to that of the hearing aid control Arm B. The familywise error rate in the secondary analyses will be controlled by a Bonferroni correction using a significance level of $p = 0.01$.

Investigating treatment effect on:

- Psychosocial measures:
 - UCLA loneliness Scale:
 - ☒ A6 vs B6
 - Geriatric Depression Scale (GDS):
 - ☒ A6 vs B6
- Audiologic measures:
 - CNC words:
 - ☒ A6 vs B6
 - AzBio Sentences:

Statistical Analysis Plan		Page 12 of 16
Sponsor Cochlear	Study Hearing Loss in Older Adults	CIP Version 9.0

☒ A6 vs B6

- Quality of life:
 - Health Utilities Index Mark III (HUI-III):
 - ☒ A6 vs B6

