6.6.1.1 Primary Analysis

The primary efficacy endpoint will be assessed with the following hypothesis:

$$H_0: \mu_A \geq \mu_B$$

$$H_a: \mu_A < \mu_B$$

Statistical Analysis Plan		Page 11 of 16
Sponsor Cochlear	Study Hearing Loss in Older Adults	CIP Version 9.0

Where μ_{A6} is the mean SSQ12 score for the cochlear implantation treatment Arm A and μ_{B6} is the mean SSQ12 score for the hearing aid control Arm B at FUV1. The hypothesis will be evaluated using a regression model with treatment and baseline score as covariates. Significance of the treatment effect will be assessed by the p-value for the treatment arm from the regression model.

For analyses using means in the primary endpoints, where there is evidence the model assumptions are not met (e.g. lack of normality of the residuals), transformations or non-parametric tests will be employed.

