6.7.1.2 Tertiary Analyses

All tertiary analyses will be presented using descriptive statistics and analyzed using a t-test to compare the mean score of the cochlear implant Arm A to that of the hearing aid control Arm B at various time points. As these tertiary analyses are exploratory in nature, there will be no adjustment for multiple comparisons, no formal hypotheses testing and no statement of statistical significance.

Investigating treatment effect on:

- Neuropsychological outcomes:
 - Cogstate¹:
 - ☒ Detection Test – speed of performance
 - ☒ Groton Maze Learning Test – number of errors
 - ☒ Identification Test – speed of performance
 - ☒ One Card Learning Test – accuracy of performance
 - ☒ One Back Test – speed of performance
 - A6 vs B6 (treatment effect)
 - A0 vs B0 (population)
 - A6 vs B12 (6 months post-CI)
 - A12 vs B18 (12 months post-CI)
 - A0 vs A6 vs A12 (longitudinal treatment effect)
 - B6 vs B12 vs B18 (longitudinal treatment effect)
 - HI-MoCA:
 - ☒ A6 vs B6 (treatment effect)
 - ☒ A0 vs B0 (population)
 - ☒ A6 vs B12 (6 months post-CI)

¹ A sensitivity analyses will be conducted with test data integrity failures excluded if the integrity failure rate is greater than 10%.

Statistical Analysis Plan		Page 13 of 16
Sponsor	Study	CIP Version
Cochlear	Hearing Loss in Older Adults	9.0

- ☒ A12 vs B18 (12 months post-CI)
- ☒ A0 vs A6 vs A12 (longitudinal treatment effect)
- ☒ B6 vs B12 vs B18 (longitudinal treatment effect)
- Psychosocial measures:
 - UCLA Loneliness Scale:
 - ☒ A0 vs B0 (population)
 - ☒ A6 vs B12 (6 months post-CI)
 - ☒ A12 vs B18 (12 months post-CI)
 - ☒ A0 vs A6 vs A12 (longitudinal treatment effect)
 - ☒ B6 vs B12 vs B18 (longitudinal treatment effect)
 - Geriatric Depression Scale (GDS):
 - ☒ A0 vs B0 (population)
 - ☒ A6 vs B12 (6 months post-CI)
 - ☒ A12 vs B18 (12 months post-CI)
 - ☒ A0 vs A6 vs A12 (longitudinal treatment effect)
 - ☒ B6 vs B12 vs B18 (longitudinal treatment effect)
- Audiometric measures:
 - HHIE-S:
 - ☒ A0 vs B0 (population)
 - ☒ A6 vs B12 (6 months post-CI)
 - ☒ A12 vs B18 (12 months post-CI)
 - ☒ A0 vs A6 vs A12 (longitudinal treatment effect)
 - ☒ B6 vs B12 vs B18 (longitudinal treatment effect)
 - SSQ12:
 - ☒ A0 vs B0 (population)
 - ☒ A6 vs B12 (6 months post-CI)
 - ☒ A12 vs B18 (12 months post-CI)
 - ☒ A0 vs A6 vs A12 (longitudinal treatment effect)
 - ☒ B6 vs B12 vs B18 (longitudinal treatment effect)

Statistical Analysis Plan		Page 14 of 16

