Sponsor Cochlear	Study Hearing Loss in Older Adults	CIP Version 9.0

[figure not shown]
- CNC words:
 - ☒ A0 vs B0 (population)
 - ☒ A6 vs B12 (6 months post-CI)
 - ☒ A12 vs B18 (12 months post-CI)
 - ☒ A0 vs A6 vs A12 (longitudinal treatment effect)
 - ☒ B6 vs B12 vs B18 (longitudinal treatment effect)
- AzBio Sentences:
 - ☒ A0 vs B0 (population)
 - ☒ A6 vs B12 (6 months post-CI)
 - ☒ A12 vs B18 (12 months post-CI)
 - ☒ A0 vs A6 vs A12 (longitudinal treatment effect)
 - ☒ B6 vs B12 vs B18 (longitudinal treatment effect)
- Audiometric thresholds
 - ☒ A0 vs B0 (population)
 - ☒ A0 vs A6 vs A12 (hearing preservation)
 - ☒ B6 vs B12 vs B18 (hearing preservation)
- Quality of life:
 - Health Utilities Index Mark III (HUI-III):
 - ☒ A0 vs B0 (population)
 - ☒ A6 vs B12 (6 months post-CI)
 - ☒ A12 vs B18 (12 months post-CI)
 - ☒ A0 vs A6 vs A12 (longitudinal treatment effect)
 - ☒ B6 vs B12 vs B18 (longitudinal treatment effect)

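### SAP 6.7.1.1 compares arm means by correlation and sets a Bonferroni level where SAP 6.7 rules out testing; SAP 6.7.1.2 gives 20 within-arm comparisons a between-arm t-test

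*SAP*

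**What the plan says.** SAP 6.7 divides the ancillary analyses into secondary and tertiary, and says of both: "No formal hypotheses testing will be conducted for the ancillary analyses".

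SAP 6.7.1.1 covers five secondary outcomes, each compared as A6 vs B6: UCLA loneliness, GDS, CNC words, AzBio sentences and HUI-III. They will be summarised descriptively and "analyzed using pairwise correlations to compare the mean score of the cochlear implant Arm A to that of the hearing aid control Arm B". It adds: "The familywise error rate in the secondary analyses will be controlled by a Bonferroni correction", at p = 0.01.

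SAP 6.7.1.2 says that all tertiary analyses use descriptive statistics and a t-test, the purpose of which is to "compare the mean score of the cochlear implant Arm A to that of the hearing aid control Arm B at various time points", with "no formal hypotheses testing and no statement of statistical significance". The list that follows includes, for each measure, one three-visit row within Arm A and one within Arm B. Examples are "A0 vs A6 vs A12 (longitudinal treatment effect") and, for audiometric thresholds, "A0 vs A6 vs A12 (hearing preservation").

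By contrast, the primary SSQ12 outcome in SAP 6.6.1.1 is analysed "using a regression model with treatment and baseline score as covariates".

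**The concern.** There are three separate faults.

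1. **Method for the five secondary outcomes.** SAP 4.1 randomises different people to the two arms, so no Arm A score belongs with any particular Arm B score. A correlation between the two sets answers a different question from a comparison of means. If the word is a slip for comparisons, no test is named at all.
2. **Status of those outcomes.** Controlling familywise error is control over wrong significance claims, yet SAP 6.7 says there is no formal testing. SAP 6.7.1.2 forbids significance statements for the tertiary rows and SAP 6.7.1.1 has no such ban. Two analysts could disagree on whether p < 0.01 on loneliness may be called significant.
3. **Method for the within-arm rows.** A test of Arm A against Arm B cannot be run on three visits from one arm.

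The Protocol Synopsis lists as ancillary aims the FUV1 effect on loneliness, depression and quality of life, pre- to post-implantation change, and maintenance of effect (FUV2 against FUV1 in Arm A, FUV3 against FUV2 in Arm B). The last two are within-arm aims. The trial is unblinded (SAP 4.2), so leaving the method and the significance status open until data are in hand invites selective reporting.

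**Working it through.** **The stated level.** SAP 6.1.3 gives a default two-sided level of 0.05, and SAP 6.7.1.1 prints five comparisons. Bonferroni level = 0.05/5 = 0.01, which reproduces the SAP's figure. Other readings do not: 0.025/5 = 0.005, and 0.01 taken as the familywise level gives 0.01/5 = 0.002. With five independent tests at 0.01 the familywise error is 1 − 0.99^5 = 0.049. The number is sound for five tests; the conflict is with SAP 6.7.

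**What a correlation would do.** One data set was simulated with 30 subjects per arm, SD 1 and a true difference of 0.6 SD (all assumed).

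- Two-sample t-test: p = 0.0155.
- Correlation of score with a 0/1 arm indicator: p = 0.0155, identical.
- Correlation of Arm A scores with Arm B scores in arbitrary row order: r = −0.160, p = 0.40.
- The same correlation after adding 3 points to every Arm A score: r = −0.160, unchanged.

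A correlation between the arms' scores does not respond to a shift in one arm's mean, so it carries no information on the treatment effect. The arm-indicator version is a valid test but does not itself report a difference in scale units.

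**Row count in SAP 6.7.1.2.**

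| Measure | Between-arm rows | Within-arm rows |
|---|---|---|
| Cogstate | 4 | 2 |
| HI-MoCA | 4 | 2 |
| UCLA, GDS, HHIE-S, SSQ12, CNC, AzBio, HUI-III (7 measures) | 7 × 3 = 21 | 7 × 2 = 14 |
| Audiometric thresholds | 1 | 2 |
| Total | 30 | 20 |

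The total is 50 rows, of which 20 (40%) are within-arm. If the Cogstate rows are expanded over its five tests, between-arm is 30 − 4 + 20 = 46 and within-arm is 20 − 2 + 10 = 28, out of 74.

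**Any within-subject method elsewhere?** None is named in the SAP. The remark in SAP 5.1.1 that subjects act as their own control specifies no analysis. If someone adapted the two-sample test by treating two visits as independent groups, then with equal variances and between-visit correlation ρ the standard error of the change would be too large by 1/√(1 − ρ): 1/√0.7 = 1.20 at ρ = 0.3 and 1/√0.3 = 1.83 at ρ = 0.7. These values of ρ are assumptions; the documents give none.

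**Are baselines available for a better model?** Protocol 5 and the table in SAP 6.1.2 both place UCLA, GDS, HUI-III, CNC and AzBio at POV2, so yes for all five.

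**The case against.** The best defence is that SAP 6.7.1.1 states its target plainly: the two arm means are to be compared. On that view one word is wrong. Descriptive statistics are planned throughout, and SAP 6.1.1 allows t-based confidence intervals where appropriate. A reader might infer that the five outcomes would be left with no usable result. The documents do not support that: arm means would still be reported, and one reading of the method gives a valid p-value. What stands is that the SAP does not state that reading, and elsewhere it writes t-test or regression when it means them.

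On testing, SAP 6.6.2 and 6.7.1.2 both pair a t-test with a statement that there is no formal testing. The phrase may therefore mean only that no null and alternative hypotheses are written out, as they are for the primary endpoint. That softens the conflict but does not remove it, because a familywise correction has a purpose only if significance will be declared.

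A reader might also infer that 0.01 is the wrong level, since Protocol 9.3.9 measures speech recognition in two listening conditions at FUV1. The SAP prints CNC once and AzBio once, and the Synopsis text on reporting both conditions belongs to the pre- to post-implantation aim. Five comparisons is what the plan lists. The fair request is to name the condition.

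For the within-arm rows, it can be said that they are exploratory, that no significance statement is allowed, and that each row prints its visits. This limits the harm. It does not make an Arm A versus Arm B test applicable.

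**Conclusion.** The point holds and should be fixed before analysis. For five of five secondary outcomes the stated method does not, as worded, compare the arm means, and whether p < 0.01 is a significance claim is unsettled. For 20 of 50 tertiary rows (28 of 74 expanded) the stated test cannot be applied, and these rows carry two of the Protocol's ancillary aims. The counts are taken from the SAP as printed and need no outside figure.

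The reach is limited. All affected analyses are ancillary. The primary SSQ12 analysis and the Cogstate secondary endpoint in SAP 6.6.2 are unaffected, and SAP 7 allows an amendment before analysis. Nothing here shows that the level 0.01 is wrong for the five comparisons listed.

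**What to change.** 1. **SAP 6.7.1.1, method.** Replace the correlation wording with the primary model: FUV1 score regressed on arm and the same measure's POV2 score, in subjects with both, reporting the adjusted mean difference (A minus B) with a confidence interval and the number analysed. A two-sample t-test, as SAP 6.6.2 and 6.7.1.2 use for A6 vs B6, is the minimum repair. Baseline adjustment is an improvement that needs no new data; its gain depends on baseline correlations the documents do not give.
2. **SAP 6.7 and 6.7.1.1, status.** Either delete the Bonferroni sentence and report estimates with 95% intervals, or state that the five outcomes are formally tested at 0.01, with matching 99% intervals. In either case name the listening condition used for CNC and AzBio. If more than one is tested, the level must be recalculated for the larger family.
3. **SAP 6.7.1.2, within-arm rows.** Limit the two-sample t-test to the between-arm rows. For the within-arm rows specify paired contrasts or a repeated-measures mixed model: A6 − A0 and B12 − B6 for pre to post, A12 − A6 and B18 − B12 for maintenance.
4. **Check before step 3.** Reconcile the HI-MoCA schedule. The table in Protocol 5 marks it only at POV1 and FUV1, whereas Protocol 9.3.13 and 9.3.14 call for the full neuropsychological battery at FUV2 and FUV3, and SAP 6.1.2 lists scores at those visits.

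Steps 1 to 3 cost SAP wording only, with no added subjects or visits. Each baseline-adjusted model uses one more degree of freedom than a t-test. Step 4 may also need a change to the Protocol text.

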Ancillary analyses	
Ancillary analyses include:
 
 Investigating treatment effect on neuropsychological measures using the Hearing Impaired Montreal Cognitive Assessment (HI-MoCA) at Follow-Up Visit 1 (FUV1). Investigate the treatment effect of immediate cochlear implantation vs continued use of HAs on psychosocial measures such as loneliness and depression using the UCLA Loneliness Scale and the Geriatric Depression Scale (GDS) at Follow-up Visit 1 (FUV1). Investigate the treatment effect of immediate cochlear implantation vs continued use of HAs on physical functioning measures such as daily activity and lifestyle using the Lifestyle Activity Questionnaire (LAQ) at Follow-up Visit 1 (FUV1). To determine the effect of treating hearing loss with CI versus continued use of HAs on quality of life in each arm (immediate CI vs continued HA use) using the Health Utilities Index Mark III (HUI-III) at Follow-up Visit 1 (FUV1). To quantify pre- to post-implantation outcomes associated with cochlear implantation. 
 Self-reported hearing ability using the Hearing Handicap Inventory for the Elderly – Screening (HHIE-S). Outcomes for both the treated ear and everyday listening condition (bimodal): speech perception in quiet using CNC Words presented 60 dBA and speech perception in speech-weighted noise using AzBio sentences presented at 65 dBA using a +10 dB Signal to Noise Ratio (SNR). Investigate maintenance of treatment effect on neuropsychological, psychosocial, physical, quality of life and audiometric measures obtained at: 
 FUV2 compared to FUV1 (Arm A). FUV3 compared to FUV2 (Arm B).

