5.1.1 Primary endpoint

The primary endpoint for the clinical investigation is assessment of the impact of cochlear implantation versus continued hearing aid use on the Speech, Spatial and Qualities of Hearing – short form (SSQ12) test measure at Follow-up Visit 1 (FUV1). Each subject will serve as their own control.

Data from a clinical investigation on the Cognitive Performance of Severely Hearing-impaired Older Adults Before and After Cochlear Implantation (1) was used to estimate the effect of cochlear implantation on the SSQ12.

The sample size estimation for the primary endpoint is based on the mean (SD) change of 3.0 (1.8) for the change in SSQ12 score reported in Claes et al. (pre-operative to postoperatively at six months post-activation) (1). The sample size estimation assumes that the observed mean change and standard deviation of change reported by Claes for SSQ12 is representative of the corresponding values for the clinical population under investigation.

Statistical Analysis Plan		Page 8 of 16
Sponsor Cochlear	Study Hearing Loss in Older Adults	CIP Version 9.0

Sample size calculations were conducted using PASS statistical software under the following general assumptions:

1. Two-sample t-test
2. Two-sided 0.025 α levels
3. 80% power
4. No accounting for attrition or lost to follow up

In order to achieve 80% power with an effect size of 1.667 ($d = (\mu_A - \mu_B)/\sigma$) with 20% attrition, a sample size of 12 per arm would be needed respectively. Therefore, a sample size of 60 supports the effect sizes observed in Claes et al. (2018) as well as possible attrition.

6 Statistical Analyses

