6.1.3 Statistical Significance

Unless otherwise specified, hypothesis testing will be performed at the two-sided 0.05 significance level (or equivalently at a one-sided 0.025 level). P-values will be rounded to three decimal places. If a p-value is less than 0.001 it will be reported as "<0.001". If a p-value is greater than 0.999, it will be reported as ">0.999".

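### SAP 6.7.1.1: single-step Bonferroni at 0.01 over five secondary comparisons is valid but needlessly strict; Holm gives the same control with more power, and the section must be reconciled with the no-formal-testing sentence in 6.7

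*SAP*

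**What the plan says.** SAP 6.7 places the secondary and tertiary analyses under one ancillary heading and states: "No formal hypotheses testing will be conducted for the ancillary analyses".

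SAP 6.7.1.1 then lists five measures, each compared between Arm A and Arm B at six months (A6 vs B6): UCLA Loneliness Scale, GDS, CNC words, AzBio sentences and HUI-III. On multiplicity it says: "The familywise error rate in the secondary analyses will be controlled by a Bonferroni correction using a significance level of" 0.01. On method it says: "All secondary analyses will be presented using descriptive statistics and analyzed using pairwise correlations to compare the mean score" of the two arms.

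The SAP's exploratory sections are worded differently. Section 6.6.2 (Cogstate) has no multiplicity adjustment and no formal testing. Section 6.7.1.2 (tertiary) has neither, and also rules out any statement of statistical significance. Section 6.7.1.1 contains no such bar.

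For the primary SSQ12 comparison, SAP 6.6.1.1 says: "Significance of the treatment effect will be assessed by the p-value for the treatment arm from the regression model". The default level in SAP 6.1.3 is two-sided 0.05, whereas the sample-size assumptions in SAP 5.1.1 list "Two-sided 0.025 α levels". No section makes the five secondary comparisons depend on the SSQ12 result.

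**The concern.** There are two issues.

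The first is efficiency. Single-step Bonferroni holds all five tests at 0.01, even after some have been rejected. The two speech tests may well show larger effects than loneliness, depression or general quality of life. If they do, the three weaker measures still face 0.01 when a stepwise procedure with identical error control would allow a larger threshold. The trial is sized for SSQ12 only, so power on these measures is limited and should not be given away.

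The second is status. A familywise error rate has meaning only if rejections are declared. Section 6.7.1.1 sets up such declarations and 6.7 says there is no formal testing. A reader of the final report could not tell whether a p-value of 0.008 on HUI-III is a controlled finding or a descriptive figure.

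**Working it through.** **Inputs from the documents.** Five A6 vs B6 measures at 0.01 each (SAP 6.7.1.1); default level two-sided 0.05 (SAP 6.1.3); at least 28 per arm and about 60 in all (SAP 4); 20% attrition (SAP 4.1), so a pessimistic case is 30 × 0.80 = 24 per arm.

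**Assumptions.** Standardised effects d from 0.5 to 1.2 on the five measures, and a common correlation of 0.5 between test statistics. The documents give neither.

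**Step 1: the plan's own figure.** 0.05/5 = 0.01. If all five nulls are true, the familywise rate is at most 5 × 0.01 = 0.05, and 1 − 0.99^5 = 0.049 if the tests are independent. The SAP's claim is met.

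**Step 2: Holm on the same five p-values.** Order them from smallest to largest and compare them in turn with 0.05/5 = 0.0100, 0.05/4 = 0.0125, 0.05/3 = 0.0167, 0.05/2 = 0.0250 and 0.05, stopping at the first failure. Every p-value at or below 0.01 is rejected, so nothing Bonferroni rejects is lost. If m of the five nulls are true, the first true null reached faces a threshold of at most 0.05/m. The chance of any false rejection is therefore at most m × 0.05/m = 0.05, whatever the correlation.

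**Step 3: power.** Two-sample t statistics were simulated with noncentrality d × √(n/2). At n = 28 (54 degrees of freedom) that is 1.87 for d = 0.5, 2.24 for 0.6, 2.99 for 0.8 and 4.49 for 1.2. Power per measure at correlation 0.5:

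| Per arm | Assumed effects | Measure | Flat 0.01 | Holm |
|---|---|---|---|---|
| 28 | all d = 0.5 | any one | 22% | 27% |
| 28 | all d = 0.8 | any one | 63% | 73% |
| 28 | speech tests 1.2, others 0.6 | each of the other three | 34% | 49% |
| 28 | speech tests 1.2, others 0.8 | each of the other three | 63% | 78% |
| 24 | all d = 0.5 | any one | 18% | 22% |
| 24 | all d = 0.8 | any one | 54% | 65% |

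The gain is largest in the mixed cases. Each speech test at d = 1.2 is rejected about 96% of the time, and after two rejections the next test faces 0.0167 rather than 0.01.

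**Step 4: what does not change.** The first Holm threshold is 0.01, so the chance of at least one rejection is identical under the two methods: 54% under both if all d = 0.5, and 92% under both if all d = 0.8 (28 per arm, correlation 0.5).

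**Step 5: context, primary plus five secondaries with every null true.** With a two-sided 0.05 primary, the bound is 0.05 + 5 × 0.01 = 0.10. Under independence the rate is 1 − 0.95 × 0.99^5 = 0.097. By simulation with equal correlations it is 0.082 at correlation 0.5 and 0.069 at 0.7. With the two-sided 0.025 in SAP 5.1.1, the bound is 0.025 + 0.05 = 0.075, and independence gives 1 − 0.975 × 0.99^5 = 0.073.

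**The case against.** The strongest defence is that flat Bonferroni is a valid method, delivers what 6.7.1.1 promises, and is applied to measures that the SAP itself calls ancillary. It also has a practical merit: 99% confidence intervals match the 0.01 tests directly, and Holm has no equally simple simultaneous intervals. The power gain rests on effects found nowhere in the documents. It is only about 5 points when all effects are moderate, and nil for the first rejection. All of this stands. The Holm point is therefore an improvement in efficiency and does not correct an error.

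A reader might go further and infer that, because the five secondaries receive their own 0.05 with no gate on SSQ12, the plan lets its false-positive rate rise to 0.08–0.10. The documents do not support calling that a failure. Section 6.7.1.1 claims control only within the secondary analyses, and no passage claims it for primary and secondary together. The range also needs a two-sided 0.05 primary and correlation no higher than about 0.5. With the 0.025 in SAP 5.1.1 the rate cannot exceed 0.075. Finally, it requires the SSQ12 null to be true. At the SAP's planning effect of 1.667, primary power exceeds 99.9% at 24 or 28 per arm, so a gate would almost never bind. That planning effect comes from a before-and-after change in a cohort, so the true between-arm effect could be smaller and a gate could then matter. This makes a gate a reasonable option without turning its absence into a defect.

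The ancillary label does not settle the status question. Sections 6.6.2 and 6.7.1.2 show that the SAP knows how to word an exploratory analysis, and 6.7.1.1 is not worded that way.

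**Conclusion.** The point holds in limited form. Bonferroni at 0.01 meets the SAP's stated claim for five tests. Holm at an overall two-sided 0.05 gives the same control under any correlation and rejects at least as much. Under the assumed effects at 28 per arm and correlation 0.5, it adds about 5 to 15 percentage points of power per measure. The size of the gain depends on those assumptions; that Holm never rejects less does not.

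The conflict between 6.7 and 6.7.1.1 over formal testing is plain on the text and needs a decision whichever procedure is used. The combined primary-plus-secondary rate (at most 0.10, or at most 0.075 with the 0.025 level) is context for that decision and breaks no guarantee in the plan.

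One condition applies throughout. The count of five assumes one score per measure. The Protocol measures CNC and AzBio in two listening conditions each, and the SAP does not say which is tested. Seven tests at 0.01 would have a bound of 0.07 (1 − 0.99^7 = 0.068 if independent), so the count should be settled.

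**What to change.** First decide the status of the five comparisons.

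**If significance statements are intended,** exempt 6.7.1.1 from the no-formal-testing sentence in 6.7 and replace the Bonferroni sentence with:

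> Across the five A6 vs B6 comparisons listed below, familywise error will be held at two-sided 0.05 by the Holm step-down procedure.

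Optionally, add that the five are tested only after a significant SSQ12 result. If that gate is adopted, reconcile the primary level (SAP 5.1.1 against 6.1.3) and the direction of the alternative in 6.6.1.1, which puts the Arm A mean below Arm B, so that the condition is well defined.

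**If they are not intended,** delete the significance level and the familywise sentence, and use the tertiary wording of 6.7.1.2. Neither Holm nor a gate is then needed.

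Holm needs one p-value per comparison. In the first case, also replace the reference to pairwise correlations with a named test of the difference between arms, and name the listening condition for CNC and AzBio.

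**Cost.** SAP wording only; no new data or participants. Holm gives up the simple matching confidence intervals. The first option gives these ancillary measures a formal status that Cogstate, the named secondary endpoint, does not have, so the sponsor should choose it deliberately. A gate would also mean that no secondary could be called significant if SSQ12 failed.

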9.2.3.2 Speech perception in quiet

The CNC Word Test (25) is a validated test used clinically and in research to assess the performance of adults with hearing aids or cochlear implants on open-set word recognition. The test consists of 10 recorded lists of 50 monosyllabic words in CD format. For this study, two lists will be administered in quiet at a level equal to 60 dBA in the sound field and scored as total number of words and phonemes correct, which will be expressed as a percentage correct for this study. Subjects will be tested using a configuration of speech at 0° azimuth in quiet (S0).

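### The secondary analyses' Bonferroni level of 0.01 fits five tests, but the SAP does not say which listening condition is tested for CNC and AzBio, and SAP 6.7 and 6.7.1.1 disagree on whether these are formal tests

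*SAP*

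**What the plan says.** SAP 6.7.1.1 lists five measures, each with a single comparison of Arm A and Arm B at FUV1: UCLA Loneliness, GDS, CNC words, AzBio sentences and HUI-III. It says the "familywise error rate in the secondary analyses will be controlled by a Bonferroni correction" and sets the level at 0.01. The overall level being protected is not stated. The method named for comparing arm means is pairwise correlations.

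The parent section, SAP 6.7, defines the ancillary analyses as the secondary and tertiary analyses together and states: "No formal hypotheses testing will be conducted for the ancillary analyses".

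The protocol's procedures table (Section 5) has two rows for CNC and two for AzBio, one for the implant ear or ear to be implanted and one for everyday listening. Both rows are marked at FUV1. Protocol 9.3.9 confirms that both conditions are assessed in both arms at that visit. Protocol 9.2.3.2 adds that the CNC test is "scored as total number of words and phonemes correct". The SAP names no listening condition in the visit table (6.1.2), the secondary list (6.7.1.1) or the tertiary list (6.7.1.2).

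**The concern.** A Bonferroni level protects the familywise rate only for a fixed list of tests. Two of the five entries here are not fully defined. CNC or AzBio in one ear alone is a different comparison from CNC or AzBio with everything the subject normally wears (implant plus hearing aid in Arm A, two hearing aids in Arm B). The effects may differ, and an analyst working from the SAP cannot tell which to run. The study is unblinded (SAP 4.2), which is a further reason to settle the choice before analysis.

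The second difficulty is the status of the results. One section rules out formal testing for this family and its own subsection sets a significance level with error control. A reader of the final report could not tell whether p < 0.01 on, say, loneliness is a confirmatory claim within a controlled family or a description.

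**Working it through.** **Inputs.** Per-test level 0.01 (SAP 6.7.1.1). General level 0.05 two-sided (SAP 6.1.3), taken here as the familywise level because 6.7.1.1 gives none. Five listed comparisons (SAP 6.7.1.1). Two listening conditions for each of CNC and AzBio at FUV1 (Protocol 5 and 9.3.9).

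**Step 1: reproduce the plan's figure.** 0.05 / 5 = 0.01, an exact match. The one-sided variant, 0.025 / 5 = 0.005, does not match. The level was evidently set for five two-sided tests.

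**Step 2: five tests, one condition each, fixed in advance.** Bonferroni bound 5 × 0.01 = 0.05. Under independence, 1 − 0.99^5 = 0.049. The stated level is right for this case.

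**Step 3: both conditions tested.** Number of tests = 3 + 2 × 2 = 7. Bound 7 × 0.01 = 0.07. Under independence, 1 − 0.99^7 = 0.068.

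**Step 4: one condition chosen after seeing the data.** If the more favourable condition is reported, the family yields a false positive whenever any of the seven p-values falls below 0.01. The bound is the same 0.07.

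**Step 5: allow for correlation.** The same subjects hear the same type of material in both conditions, so independence is pessimistic. The documents give no correlations, so a range was assumed and seven normal test statistics were simulated (2,000,000 draws per row):

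| Correlation among the four speech tests | All other correlations | Familywise rate, 7 tests at 0.01 |
|---|---|---|
| 0.5 | 0 | 0.064 |
| 0.7 | 0 | 0.059 |
| 0.5 | 0.3 | 0.061 |
| 0.7 | 0.3 | 0.056 |
| 0.7 | 0.5 | 0.051 |
| 0.8 | 0.5 | 0.048 |
| 0.9 | 0.7 | 0.038 |

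The rate falls below 5% only when correlation is strong throughout.

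**Step 6: compare the status statements.** For Cogstate (SAP 6.6.2) and the tertiary analyses (SAP 6.7.1.2), the SAP disclaims both multiplicity adjustment and formal testing; 6.7.1.2 also disclaims any statement of significance. SAP 6.7.1.1 has no such disclaimer and sets a level instead. This suggests the five secondary comparisons were meant to be tested, but the general statement in 6.7 covers them too. Both cannot stand.

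**Step 7: check the named method.** A correlation measures association between two variables. It is not the usual way to test a difference between two arm means, and the SAP does not say which variables would be correlated. The p-value to be set against 0.01 is therefore undefined.

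**The case against.** The strongest reply is that the SAP lists five comparisons, one line each, and 0.01 is exactly right for five. Measuring two conditions does not commit the trial to testing both. SAP Section 7 allows an amended SAP approved before analysis, so a condition can still be fixed in time. The worst-case excess for seven tests is two percentage points, in ancillary analyses. All of that stands.

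Two stronger readings are tempting. A reader might infer that the claimed control already fails. The documents do not support that: on the list as written, with one condition fixed in advance, the bound is 5%. The synopsis phrase "Outcomes for both the treated ear and everyday listening condition (bimodal" does not change this, because it belongs to the aim of quantifying change from before to after implantation, not to the between-arm comparison.

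A reader might also count nine tests by adding CNC phoneme scores in both conditions. The SAP lists only CNC words, and phonemes appear only in the protocol's description of scoring. No between-arm phoneme comparison is planned anywhere. The label could be the test's name rather than its score, which is a reason to state the score but no basis for a nine-test figure.

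The reply does not remove two points: the condition is unspecified, and 6.7 contradicts 6.7.1.1.

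**Conclusion.** The arithmetic behind 0.01 is sound for five tests. The defect is under-specification together with a contradiction. With no condition named for CNC or AzBio, control at 5% is possible but not guaranteed. If both conditions are tested, or one is picked after the fact, the bound is 7%. The familywise rate would then be 6.8% under independence and about 5.6% to 6.4% under moderate assumed correlation (0.5 to 0.7 among speech tests, 0 to 0.3 elsewhere). These figures assume a familywise level of 0.05 two-sided, taken from SAP 6.1.3.

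The inflation is modest. The conflict over formal testing matters more, because it decides what the trial may conclude from these five measures, and it holds whatever the test count. The changes should be made before analysis.

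**What to change.** Amend SAP 6.7 and 6.7.1.1 before the data are analysed:

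1. For CNC, name one listening condition and the word score. For AzBio, name one condition. Make the other condition descriptive. Alternatively, list all seven comparisons as the family.
2. State the familywise level (0.05 two-sided) and apply Holm's step-down procedure in place of a fixed 0.01. With five tests the ordered p-values are compared with 0.05/5 = 0.01, 0.05/4 = 0.0125, 0.05/3 = 0.0167, 0.05/2 = 0.025 and 0.05, stopping at the first failure. Error control is the same as Bonferroni and power is never lower. Holm still needs the fixed list in item 1.
3. Either exempt this named family from the statement in 6.7 that rules out formal testing, or delete the Bonferroni sentence and report the five comparisons as descriptive.
4. Replace pairwise correlations with a named between-arm comparison. A regression on arm and baseline score, as SAP 6.6.1.1 uses for SSQ12, is available, since SAP 6.1.2 shows a baseline value for all five measures.

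The cost is SAP wording only, with no new visits, data or subjects. If all seven tests are kept, the first Holm threshold tightens from 0.01 to 0.05/7 = 0.0071.
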